2.1.1. Trial Schema

Figure 1: Trial Schematic Diagram

AP=antipsychotic; EOT=end of treatment; IM=intramuscular; IR=immediate-release; OLZ=olanzapine; sc=subcutaneous; SD=single-dose; SRC=safety review committee; WO=washout

2.2. Randomization and Blinding

This is an open-label, randomized, parallel-group study. Qualified subjects who meet the trial inclusion criteria and do not meet exclusion criteria are enrolled into the trial. Approximately 2-4 participants will be assigned into the sentinel cohort 1A (TV-44749 425 mg Fast-D), which will be the first cohort to proceed to Period 3, TV-44749 treatment period. Upon completion of the first 15 days in Period 3 (day R1 to day R15, inclusive) following sc administration of olanzapine Fast-D formulation to cohort 1A participants, a SRC will review all available safety and tolerability data from the beginning of the study, as described in Section 2.1. If no safety concern is raised by the SRC, randomization will be initiated to cohort 1B (TV-44749 425 mg Fast-D, n~16), cohort 2 (TV-44749 425 mg to-be-marketed, n~20) and cohort 3 (n~20) at a randomization ratio of 4:5:5.

The specifications for randomization will be under the responsibility and oversight of Teva Global Statistics. The randomization list will be generated by a qualified service provider under the oversight of Teva Global Statistics.

2.2.1. Maintenance of Randomization

Participant randomization codes will be maintained by the service provider contracted to generate the codes.

2.2.2. Blinding and Unblinding

This is an open-label trial. The study will be treated as open-label for all cohorts.

2.3. Data Monitoring Committee

2.3.1. Safety Review Committee

An SRC comprising the Sponsor's clinical trial physician, clinical leader, PV physician, and other relevant experts defined in the SRC Charter will be summoned to review all safety data (including demography, vital signs, clinical laboratory tests and ECGs, AEs, concomitant medications use, local tolerability and pain, leakage assessment) available upon from the beginning of the study to completion of the first 15 days, inclusive of the sentinel cohort (cohort 1A). Following SRC decision that no safety concerns are raised based on the safety review of cohort 1A safety data up to day R15, inclusive, period 3 for cohort 1B may be initiated. Randomization to cohorts 2 and 3 will be initiated in parallel to cohort 1B.

2.3.2. Adjudication Committee

In the case of a suspected post-injection delirium/sedation syndrome (PDSS) event, an adjudication committee will be summoned to review all cases of suspected PDSS to determine if each case fulfills all five criteria in the definition for a clinical diagnosis of PDSS (adapted from [Detke et al 2010](#)), as well as to evaluate the robustness of the available clinical evidence.

Further details are provided in Section 10.2 of the trial protocol.

2.4. Sample Size Determination

The planned sample size for this trial is approximately 95 enrolled adult participants in order to achieve approximately 60 completers (approximately 20 participants per each single-dose Olanzapine extended-release cohort). Completers are defined as participants who have completed the procedures and assessments required through follow-up period of sc olanzapine ER (ie, the 84 days after the sc injection, up to and including day R84).

Given the descriptive and exploratory nature of the trial, which is intended to collect concentration/pharmacokinetic data for an IVIVC analysis and modelling to be carried out by an external service provider, no formal sample size calculation has been performed for this trial.

If a participant is enrolled but terminates the trial early (for criteria of ET, see Section 7.1 of the trial protocol), or has events that would affect the calculation of PK parameters, an additional patient may be enrolled to ensure that at least 20 participants per group have completed the PK portion of the trial and can be considered evaluable for the primary analysis of the trial (see Section 3.2).

2.5. Sequence of Planned Analyses

2.5.1. Planned Interim Analyses

No formal interim analysis is planned in this open-label Phase 1 trial. Review of sentinel cohort 1A data prior to dosing cohort 1B by the SRC is described in Section 2.3.1.

The Sponsor may leverage preliminary concentration data to initiate IVIVC modeling activity prior to database lock, without impacting the study conduct.

2.5.2. Final Analyses and Reporting

All analyses identified in this Statistical Analysis Plan will be performed after the end of trial as defined in the trial protocol.

This Statistical Analysis Plan and any corresponding amendments will be approved before database lock, in accordance to SOP GSD-SOP-702 (Statistical Analysis Plan).

3. ANALYSIS SETS

3.1. Enrolled Analysis Set

The enrolled analysis set will include all participants who sign an ICF and are enrolled in the trial. This analysis set will be used for summarizing demography and baseline data.

3.2. Pharmacokinetics Analysis Set

The PK analysis set will include all participants who have sufficient data to calculate at least one PK parameter for any of the olanzapine formulations (IM immediate release or sc ER) and have no intercurrent events or deviations that would affect the calculation of PK parameters. This analysis set will be used for all PK summaries. In the PK analysis set, cohorts will be assigned based on the formulation that the participants actually received, regardless of the cohort they were randomized to, unless otherwise specified.

A drug metabolism and PK (DMPK) scientist and a clinical pharmacologist will identify each individual participant's PK parameters to be included in the analysis. Individual PK parameters that are considered outliers (e.g. parameters that were based on partial data) will be excluded from the primary analysis. Any exclusion of PK parameters will be justified in the PK parameter raw data file provided by the DMPK. A Data Review meeting will be held prior to database lock of the trial, and any protocol deviations that could potentially impact the PK will be identified. In case intercurrent events which could adversely affect the calculation of the PK parameters for any of the participants are identified, the participant may be excluded from the primary and secondary PK analyses. A leakage score of 4 after TV-44749 sc administration will result in exclusion from the PK analysis set. Data from excluded participants will be included in the relevant listing.

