4.2. Rationale for Trial Design

The trial design follows the recommendations provided in the FDA Guidance for Industry: Extended Release Oral Dosage Forms: Development, Evaluation, and Application of In Vitro/In Vivo Correlations (FDA, 1997). The objective of developing an IVIVC is to establish a predictive mathematical model describing the relationship between an in vitro property (usually the rate or extent of drug dissolution or release) and a relevant in vivo response (plasma drug concentration or amount of drug absorbed), per the FDA guidance (FDA, 1997) on the development, evaluation and application of IVIVC for extended-release oral products.

With the purpose of establishing IVIVC, the PK of 3 olanzapine extended-release sc formulations with different release rates will be characterized following a single-dose administration in participants with schizophrenia or schizoaffective disorder. The trial design will include extensive characterization of the PK profiles over 84 days after olanzapine sc administration (day R1 to day R84) to characterize fully the absorption kinetics of all 3 formulations for the purpose of IVIVC. All 3 formulations are expected to provide extended-release of olanzapine during the 84-day treatment period following single-dose sc administration and are expected to differ only in C_{max} as a consequence of a different release rate, with no burst present. The trial design also includes a single-dose administration of ZYPREXA im, before sc administration of one of the 3 sc olanzapine extended-release formulations. The obtained PK data of this im immediate-release formulation will be used to characterize olanzapine disposition for the purpose of IVIVC analysis. These analyses will be conducted and reported separately from the main trial results.

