9.8. Sample Size Determination

The planned sample size for this trial is approximately 95 enrolled participants in order to achieve approximately 60 completers (approximately 20 participants per cohort). Completers are defined as participants who have completed the procedures and assessments required through

follow-up period of sc olanzapine ER (ie, the 84 days after the sc injection, up to and including day R84).

Given the descriptive and exploratory nature of the trial, which is intended to collect pharmacokinetic data for an IVIVC external analysis, no formal sample size calculation has been performed for this trial.

If a participant is enrolled but terminates the trial early (for criteria of ET, see Section 7.1), or has events that would affect the calculation of PK parameters, an additional patient may be enrolled to ensure that approximately 20 participants per group have completed the PK portion of the trial and can be considered evaluable for the primary analysis of the study (see Section 9.1.2).

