To characterize the pharmacokinetics of immediate-release ZYPREXA im in participants with schizophrenia or schizoaffective disorder.	
The following pharmacokinetic parameters will be calculated for ZYPREXA im to support the secondary objective of the trial:
 
 • C_{max} over the 24-hour period following single-dose administration of the im formulation (day 4) • AUC following single-dose administration of ZYPREXA im to last measurable concentration (AUC_{0-t}) (day 4 to day 13) • Apparent plasma terminal elimination rate constant (λ_z) over the 216-hour period (9 days) following single-dose administration of ZYPREXA im (day 4 to day 13)

^a Day R29 is considered inclusive when referencing the completion of Period 3 assessments. Thus, for the purpose of analysis, assessments associated with Period 3 are defined from Day R1 up to and including the assessments performed at Day R29 that are prior to returning a participant to antipsychotic treatment (see footnote b, Table 5 from the study protocol).

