6. PHARMACOKINETIC ANALYSIS

6.1. General

The pharmacokinetic analysis set will be used for all plasma concentration descriptive summaries, graphs, and listings and for PK parameter listings, unless otherwise stated. The pharmacokinetic analysis set will be used for parameter descriptive summaries, graphs, and statistical analyses, unless otherwise stated. No formal inferential statistical analyses of PK data are planned.

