6.5. Pharmacokinetic parameters

Pharmacokinetic parameters will be calculated from individual olanzapine plasma concentrations, actual elapsed time profiles by non-compartmental methods, when possible. The PK parameters detailed in [Table 1](#) will be calculated following ZYPREXA im administration. Additional PK parameters may be calculated if deemed necessary.

Table 1: Description of Pharmacokinetic Parameters Following Zyprexa IM Administration

Pharmacokinetic Parameter	Description
C_{max}	Maximum observed plasma drug concentration (C_{max}) over the 24-hour period following single-dose administration of ZYPREXA im (day 4), obtained directly from the observed concentration time data
AUC_{0-t}	AUC following single-dose administration of ZYPREXA im to last measurable concentration (AUC_{0-t}) (pre-dose ZYPREXA im to 216 hours post im administration); calculated by lin- up log down trapezoidal method
λ_z	apparent plasma terminal elimination rate constant (λ_z), estimated by linear regression of the terminal portion of the log-concentration by time curve;
███████████	███████████
███████████	███████████
$AUC_{0-\infty}$	AUC extrapolated to infinity ($AUC_{0-\infty}$) calculated from last measurable plasma concentration following single dose administration of ZYPREXA im (pre-dose ZYPREXA im to 216 hours post im administration); calculated by linear-up log-down method
███████████	███████████
████	███████████
████	███████████
████	███████████

The PK parameters detailed in [Table 2](#) will be calculated following sc olanzapine extended -release formulation administration. Additional PK parameters for olanzapine extended -release formulation may be calculated if deemed necessary.

Table 2: Description Of Pharmacokinetic Parameters Following sc Olanzapine Extended-Release Formulation Administration

Pharmacokinetic parameters will be individually listed and summarized for each treatment and cohort (ZYPREXA im, and Olanzapine sc extended-release formulations) using descriptive statistics (n, mean, standard deviation, geometric mean [if appropriate], geometric coefficient of variation (%CV) [if appropriate], median, minimum, and maximum).

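### Because SAP 3.2 uses one PK set for both routes, a leakage score of 4 after the sc injection also removes the participant's earlier, unaffected ZYPREXA im data from the im summaries

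*SAP*

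**What the plan says.** SAP 3.2 sets up one PK analysis set for both routes. A participant enters with "sufficient data to calculate at least one PK parameter for any of the olanzapine formulations (IM immediate release or sc ER", provided that no intercurrent event or deviation would affect the parameter calculation. On its use, the section says: "This analysis set will be used for all PK summaries". On leakage it says: "A leakage score of 4 after TV-44749 sc administration will result in exclusion from the PK analysis set". Excluded participants' data are kept for the relevant listing.

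SAP 6.1 applies the same set to concentration summaries and graphs, and for parameters says: "The pharmacokinetic analysis set will be used for parameter descriptive summaries, graphs, and statistical analyses, unless otherwise stated". SAP 6.5 adds: "Pharmacokinetic parameters will be individually listed and summarized for each treatment and cohort (ZYPREXA im, and Olanzapine sc extended-release formulations".

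Protocol 6.3 and 9.1.2 carry the same set-level leakage exclusion. No visible section of either document defines a separate im set or exempts im data from the rule.

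The im data serve a stated secondary objective (SAP 1.1): "To characterize the pharmacokinetics of immediate-release ZYPREXA im in participants with schizophrenia or schizoaffective disorder".

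**The concern.** The leakage rule concerns a failed sc injection, but it acts on the participant and not on the sc data. A participant may have a complete im profile and then a score of 4 on day R1. That profile is lost from the secondary-objective summaries because of an event that came after it.

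The rule is also uneven. Someone who leaves the trial before the sc injection can stay in the PK set on im data alone. Someone with the same im data who goes on to a leaking sc injection is removed.

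At stake are valid im profiles in the descriptive im tables and plots. The sc tables are not in question: leaving a score-4 injection out of them is reasonable.

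**Working it through.** **1. Which data the rule reaches.** SAP 3.2 makes the set participant-level, uses it for all PK summaries, and makes removal mandatory for score 4. SAP 6.1 allows exceptions only where stated, and none is stated for im data. The im data of a score-4 participant therefore leave the summaries and graphs.

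**2. Whether the leak could affect the im data.** The im AUC and terminal-rate measures run to 216 h after the im dose (Protocol 3.1). Participants going straight to period 3 give the 216 h sample before sc dosing. Those with an extended period 2 give it on day 13, also before R1 (Protocol 4.1 and Table 6; SAP 2.1). The whole im profile precedes the sc injection, so the leak cannot change it.

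**3. How the rule treats two participants with the same im data.**

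| Participant | im profile | sc injection | In the PK set? |
|---|---|---|---|
| Leaves before R1 | complete | none | Yes, on im data alone |
| Leakage score 4 on R1 | complete | failed | No |

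**4. Precision lost.** The plan has no figure to reproduce; Protocol 9.8 and SAP 2.4 report no formal sample size calculation. The target is "The planned sample size for this trial is approximately 95 enrolled participants in order to achieve approximately 60 completers", about 20 per cohort. Suppose score-4 participants are replaced, so that n evaluable participants remain after k are dropped. Keeping the k im profiles would give n + k. The relative increase in standard error from dropping them is

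sqrt((n + k)/n) − 1

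| im summary | k = 1 | k = 2 | k = 3 |
|---|---|---|---|
| Pooled, n = 60 | sqrt(61/60) − 1 = 0.8% | sqrt(62/60) − 1 = 1.7% | sqrt(63/60) − 1 = 2.5% |
| By cohort, n = 20 | sqrt(21/20) − 1 = 2.5% | sqrt(22/20) − 1 = 4.9% | sqrt(23/20) − 1 = 7.2% |

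Non-completers with im data may also enter the im summaries, so the pooled number can exceed 60. At the limit of 95 in total, sqrt(95/(95 − k)) − 1 gives 0.5%, 1.1% and 1.6%.

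**5. How often it might happen.** The documents give no score-4 rate, so the rates p below are assumed. With 60 participants dosed sc, the expected number of im profiles lost is 60p, and the chance of losing at least one is 1 − (1 − p)^60.

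| Assumed rate | Expected profiles lost | Chance of at least one |
|---|---|---|
| 0.5% | 0.3 | 26% |
| 1% | 0.6 | 45% |
| 2% | 1.2 | 70% |
| 5% | 3.0 | 95% |

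If the exclusion applied to sc data only, leakage would remove no im profile at any rate.

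**The case against.** The best defence is that the rule is pre-specified, stated alike in Protocol 6.3, Protocol 9.1.2 and SAP 3.2, and nearly weightless. The PK summaries are descriptive with no inference, excluded data are still listed, and a replacement participant also receives ZYPREXA im. All of that stands. It limits the size of the point but gives no reason to discard unaffected data.

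Two provisions in SAP 3.2 might seem to rescue the im data. The DMPK scientist and clinical pharmacologist choose which parameters enter the analysis, but choosing parameters does not restore a participant already removed from the set. The general intercurrent-event sentence is discretionary, whereas the leakage sentence is mandatory.

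The by-cohort figures are less certain than the pooled ones. SAP 6.5 can be read as summarising im parameters by cohort, but SAP 6.4 plots ZYPREXA im separately and attaches the cohort split to the sc formulations. The standard error is also absent from the PK statistics listed in SAP 6.3 and 6.5, so the percentages measure precision and need not appear in a table.

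A reader might draw three stronger conclusions that the documents do not support:

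- **The rule undermines the IVIVC.** Protocol 4.2 does say: "The obtained PK data of this im immediate-release formulation will be used to characterize olanzapine disposition for the purpose of IVIVC analysis". But that analysis is separate, and the documents do not say whether it uses this PK set.
- **Score 3 is left unhandled.** It has no leakage-specific rule, but the no-intercurrent-event condition and the DMPK review in SAP 3.2 cover it. Fixing in advance that such participants stay in the sc tables would conflict with that condition and with the primary estimand population in SAP 1.2.
- **The SAP ignores the end-of-leakage score.** SAP 7.7 describes only the immediate assessment, but its summary sentence is not limited to it.

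**Conclusion.** The point holds and is minor. As written, SAP 3.2 removes valid secondary-objective im data because of a later sc event, and nothing visible in either document prevents this. The expected consequence is a small loss of precision in the im summaries: about 0.8% to 2.5% in standard error for one to three cases with 60 pooled, or 2.5% to 7.2% in a by-cohort summary of about 20.

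These figures assume that replacement keeps the evaluable target met and that one to three cases occur. There may be none. Taking the effect as lost precision and not bias assumes that leakage at the sc site is unrelated to a participant's im pharmacokinetics; the documents suggest no link.

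A separate administrative inconsistency should be cleared up at the same time. Protocol 6.3 and 9.1.2 make replacement of a score-4 participant definite, while Protocol 8.14 makes it optional. These passages must be reconciled. This does not change which im data are excluded.

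**What to change.** Before database lock, amend the leakage sentence in SAP 3.2 to say, in substance:

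> A leakage score of 4 at either the immediate or the end-of-leakage assessment (Protocol 8.14) excludes the participant from the sc olanzapine PK summaries and graphs only. The participant's ZYPREXA im data remain in the ZYPREXA im summaries and graphs.

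Align the exclusion wording in Protocol 6.3 and 9.1.2, or explain the difference in the CSR, as the SAP Introduction provides. Reconcile the replacement wording across Protocol 6.3, 8.14 and 9.1.2. Leave score 3 under the existing intercurrent-event and DMPK review.

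The cost is wording only, with no new data or visits. The one downside is that the im and sc summaries would no longer rest on the same participants, so each table must show its own n. The planned PK summaries already report n.

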3.3. Safety Analysis Set

The safety analysis set will include all participants who receive at least 1 dose of IMP (ZYPREXA im or one of the Olanzapine sc extended-release formulations). This analysis set will be used for all safety summaries.

In the safety analysis set, cohorts will be assigned based on the formulation that the participants actually received, regardless of the cohort they were randomized to, unless otherwise specified.

3.4. Pharmacogenomics Analysis Set

4. GENERAL ISSUES FOR DATA ANALYSIS

4.1. General

Descriptive statistics for continuous variables include number of subjects (n), mean, standard deviation (SD), standard error (SE), median, minimum, and maximum. For pharmacokinetic data, descriptive statistics will also include geometric mean (GM) and % geometric CV.

Descriptive statistics for categorical variables include number of subjects (n) and percentages, missing category will be displayed as appropriate.

4.2. Specification of Baseline Values

Baseline values are defined as the last observed data before the first dose of the trial drug, i.e. Zyprexa im or one of the sc Olanzapine extended-release formulations. For Zyprexa im, the assessments which will serve as baseline values will be based on samples collected up to and including Day 4, as long as the samples are collected prior to dosing of ZYPREXA im. For Olanzapine extended-release formulations, Day R1 (pre-dose of the sc Olanzapine extended-release formulations) assessments will serve as baseline values, except for clinical scales ([REDACTED], [REDACTED], [REDACTED] and [REDACTED]) to which day 12 will serve as baseline.

4.3. Handling Withdrawals and Missing Data

Missing data will not be imputed. In general, for all variables only the observed data from the patients will be used in the statistical analyses.

4.4. Trial Days and Visits

The trial will consist of a screening period (up to 40 days), a 3-day AP washout (WO) period (day 1 to day 3), a 1-day treatment period with immediate-release ZYPREXA im (period 1: day 4), an 8-day follow-up period (period 2: day 5 to day 12) with an optional extension of additional maximum 7 days, a 28-day treatment period with 1 of the 3 extended-release sc olanzapine formulations (period 3: day R1 to day R29), and an up to approximately 8-week follow-up period (day R29 to day R84).

Trial days will be numbered relative to the WO period on day 1 (ie, ..., -2, -1, 1, 2, ...; with day 1 of the washout period of antipsychotics and day -1 being the day before the first day of washout) and the end of the screening period. The trial days will be numbered relative to the TV-44749 administration on day R1 in Period 3 (ie, R1, R2, ...; with day R1 of the TV-44749 administration period and day R29 to day R84 of the follow-up period).

For by visit (time point) summaries, if there are multiple assessments at a post-baseline visit (time point), then the last non-missing assessment at that visit (time point) will be used for the summary (this includes both scheduled and unscheduled assessments). In general, for the by-visit summaries, Early-Termination (ET) visit will be presented as a separate visit, per study periods as follows; if the ET visit occurred between Day 4 to Day R1 (prior to the administration of TV44749) it will be mapped to "ET visit prior to TV44749 administration", if it has occurred between day R1 to day R29 it will be mapped to "ET visit during TV44749 treatment" and in case ET visit has occurred between Day R30 to Day R84 it will be mapped to "ET visit during TV44749 follow-up period". For the 'at any time' summary statistics in the shift tables and in the

presentation of Potentially Clinically Significant (PCS) summaries, all visits will be used (including unscheduled visits).

